4.9.3 Deaths

Details of any deaths will be presented in the form of an individual patient listing.

4.9.4 Laboratory Data

4.9.4.1 Safety Laboratory Parameters

All laboratory data will be converted to SI units. The Safety Laboratory Data Standardization will be used to implement reference ranges and marked abnormalities for laboratory data where possible.

Summary statistics for the absolute and change from baseline values will be produced by visit for laboratory parameters.

Marked abnormalities will be summarized for laboratory parameters. Summaries by National Cancer Institute Common Terminology Criteria for Adverse Events (NCI-CTCAE) grade will also be produced for lab assessments, including shift tables from baseline to highest grade post-baseline.

Shift tables from baseline to highest NCI-CTCAE grade post-baseline will be produced for liver function laboratory tests.

Positive pregnancy results will be listed, as identified using the serum test results, where the data will be taken from CRF “pregnancy report” page.

4.9.4.2 Immunoglobulins

The absolute values and change from baseline will be summarized by treatment group and visit for total Ig, IgA, IgG, and IgM.

The proportion of patients with a value of total Ig, IgA, IgG, and IgM which is less than the lower of limit of normal per visit will be produced.

A plot of the mean value over time will be produced for total Ig, IgA, IgG, and IgM. The plots will display error bars (mean \pm standard deviation) around the mean.

Rituximab—F. Hoffmann-La Roche Ltd
32/Statistical Analysis Plan WA29330

4.9.4.3 Lymphocyte Populations

The following NK, T and B lymphocytes will be analyzed via flow cytometry:

- CD19
- CD3
- CD4
- CD8
- Naïve B cells (CD19+ CD27-)
- Transitional B cells (CD24^{high}CD38^{high})
- Memory B cells (CD19 + CD27 +)
- NK cells (CD56+)

The absolute, change and percent change from baseline values will be summarized by visit and treatment group for the above lymphocyte populations.

The proportion of patients with a lymphocyte value less than the lower limit of normal by visit and treatment group will be produced for the following lymphocytes:

- CD3
- CD4
- CD8
- CD19

A plot of the mean and median values over the 52-week treatment period will be produced for the following:

- CD19
- CD3
- CD4
- CD8

Plots will display error bars (mean ± standard deviation) around the mean.

Patients who received rituximab rescue therapy will be analyzed separately.

4.9.4.4 Desmoglein-1 and Desmoglein-3 Autoantibody Titers

Plots of mean anti-Dsg1 and anti-Dsg3 titers over the 52-week treatment period will be produced by treatment group, along with summary statistics. Listings will include positive/negative status.

Patients who received rituximab rescue therapy will be analyzed separately.

Rituximab—F. Hoffmann-La Roche Ltd
33/Statistical Analysis Plan WA29330

4.9.4.5 Anti-Drug Antibodies

The proportion of patients that are ADA (anti-rituximab antibodies [referred to as HACA in the protocol]) positive/negative at each visit will be summarized by treatment group. A listing of ADA results will be produced.

Depending on patient counts, subgroup analyses on ADA positive patients may be carried out on key safety and efficacy variables. Such analyses may include AEs, SAEs, IRRs, CD19, and remission endpoints before/after ADA positivity.

4.9.5 Vital Signs

Vital signs are measured at baseline, Week 52, and at infusion visits immediately prior to an infusion and then every 30 minutes until the end of the infusion.

Summary tables for the absolute value and change from baseline in vital sign assessments will be presented by visit up to Week 52. Abnormal results will also be summarized. Vital sign assessments include respiratory rate, pulse rate, temperature, systolic and diastolic blood pressure. Body weight will be measured at baseline, Week 24, and Week 52. Body mass index will be calculated for these time points.

4.10 DATA HANDLING METHODS

4.10.1 Presentation of Data

Data displays include listings, tables, and plots. All data displays will be presented by treatment group.

Data presented in summary tables will be displayed using summary statistics. Continuous data will include number of patients, mean, standard deviation, median, minimum, and maximum. Categorical data will include the number and percentage of patients.

4.10.2 Definitions

Baseline

Baseline is defined as the last non-missing value prior to receipt of study treatment. Typically, baseline will be the pre-dose Day 1 assessment, but may include screening results if the pre-dose Day 1 result is not available or missing. If the Day 1 or screening result is missing then no imputation will be made and the baseline result will be set to missing.

Study Day

For each patient, the first day of study treatment will be designated study day 1. Each subsequent assessment will be assigned a study day calculated as:

$$\text{date of assessment} - \text{date of first dose} + 1$$

4.10.3 Multiple Values

For summaries displayed by visit, multiple values for a given assessment within a time window will be handled as follows:

Safety and Efficacy

The nearest non-missing value to the nominal timepoint will be assigned to the visit. If two values are equidistant from the nominal timepoint then the latest value will be selected.

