1.2.5 Rituximab Clinical Pharmacodynamics

RA patients showed near-complete depletion of peripheral CD19+ B cells by 2 weeks after the first dose, with no differences observed between the 2×1.0 g and 2×0.5 g doses of rituximab. In the majority of patients, peripheral B-cell depletion was maintained over the 24 weeks, with only a small proportion of patients showing signs of peripheral B-cell recovery by Week 24, when serum rituximab concentrations fell below 1–10 $\mu\text{g/mL}$. The extent and duration of B-cell depletion were similar for each treatment course. Repeat treatments were given on the basis of clinical symptoms and not on patients' CD19+ cell counts, which may or may not have returned to the lower limit of normal or baseline value.

Levels of total Ig, IgA, IgG, and IgM decreased in patients who received rituximab compared with those who received placebo. Mean immunoglobulin levels generally remained within the normal range.

T-cell counts remained stable after a transient decrease, likely because of concomitant RA treatment with corticosteroids. Treatment with rituximab did not appear to have an effect on serum complement, antinuclear antibody titer, or protective immunity to common infectious agents in patients with RA.

Rituximab—F. Hoffmann-La Roche Ltd
24/Protocol WA29330, Version 5

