Appendix 1 Schedule of Assessments (cont.)

-
- ^d All women who are not postmenopausal (≥ 12 months of non-therapy-induced amenorrhea) or surgically sterile will have a serum pregnancy test at screening. Urine pregnancy tests will be performed at specified subsequent visits. If a urine pregnancy test is positive, it must be confirmed by a serum pregnancy test. Prior to starting study drug, female patients of childbearing potential must have two negative pregnancy tests. The second test on Day 1 prior to randomization should be performed 8 to 10 days after the first test during the screening period.
- ^e Includes evaluation of the head, eyes, ears, nose, and throat, and the cardiovascular, dermatological, musculoskeletal, respiratory, gastrointestinal, genitourinary, and neurologic systems. Record abnormalities observed at baseline on the eCRF. Record new or worsened clinically significant abnormalities on the Adverse Event eCRF.
- ^f Includes respiratory rate, pulse rate, temperature, and systolic and diastolic blood pressure while the patient is in a seated position.
- ^g Vital signs should be taken immediately prior to infusion and then every 30 minutes until completion of the rituximab or rituximab placebo infusion.
- ^h If screening chest radiographs taken within the past 3 months show no clinically significant abnormality, further radiographic assessment is not required.
- ⁱ The DLQI, PGIC, EQ-5D-3L, and Skindex-29 will be completed by the patient before any other non-PRO assessments and before the patient receives any disease-status information or study drug during that visit. The CGIC, where possible, will be completed prior to the completion of other non-PRO assessments.
- ^j To be captured on the eCRF.
- ^k After informed consent has been obtained but prior to initiation of study drug, only serious adverse events caused by a protocol-mandated intervention should be reported. In addition, any adverse events occurring during any corticosteroid dose adjustment during the screening period should be reported.
- ^l See [Appendix 2](#).
- ^m Includes WBC count, RBC count, hemoglobin, hematocrit, platelet count, and differential (neutrophils, eosinophils, basophils, monocytes, lymphocytes, and other cells).
- ⁿ Samples to be collected prior to administration of IV methylprednisolone or saline solution and 30 minutes following completion of rituximab or rituximab placebo infusion, respectively.

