- ^o Includes sodium, potassium, chloride, bicarbonate, glucose (except at 30 minutes following completion of study drug infusion at Weeks 1, 2, 24, and 26), BUN or urea, creatinine, total protein, albumin, phosphorus, calcium, total and direct bilirubin, alkaline phosphatase, ALT, AST, uric acid, and LDH.
- ^p Dipstick for blood, protein, and glucose (microscopic examination at central laboratory if abnormal and applicable).
- ^q See Section [4.5.6](#) for T- and B-cell assessments.
- ^r Total Ig, IgG, IgA, and IgM.
- ^s Anti-Dsg1 and anti-Dsg3 antibodies.
- ^t On infusion days, PK samples will be collected prior to administration of IV methylprednisolone or saline solution and 30 minutes following

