4.6 VISIT WINDOWS

In general, data for assessments that are collected by scheduled visits will be mapped to visits that appear in the schedule of assessments per the protocol using the actual study day of assessment. Data mapped to scheduled visits will include all data collected up to the reporting cut-off date, and may include withdrawal visits and unscheduled visits.

Data will never be mapped to visits for which the assessment was not scheduled in the protocol (i.e., results for an assessment conducted at an unscheduled visit will be mapped to the appropriate visit at which the assessment was scheduled). Visit windows will be continuous from the midpoint between two consecutive study visits, and will be dependent on the schedule of assessments for each variable independently. An example of the DLQI visit window is given in [Table 1](#). Visit windows for each variable will be constructed in the same manner.

Table 1 Time Windows of Study Days to Assign Study Visit (for DLQI)

Study Visit	Scheduled Study Day (±3 days)	Time Window (Days)
Baseline	1	≤1
Week 12	84	>1 to ≤126
Week 24	168	>126 to ≤224
Week 40	280	>224 to ≤322
Week 52	364	>322 to ≤375

DLQI = dermatology life quality index.

Derived variables such as remission endpoints or assessments that are collected on an ongoing basis, such as flares and oral corticosteroid dose, will be presented using appropriate time intervals.

Data displays that are presented by visit will only include visits at which the assessment was scheduled to be collected. The methods for handling multiple values within a visit window are described in Section 4.10.3.

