Appendix 3 Schedule of Assessments (cont.)

Week	Screen (-28 to -1)	1	2	4	8	12	16	20	24	26	32	40	48	52	WD ^a	SFU ^b
Day		1 (BL and Rz)	15 ±1	28 ±3	56 ±3	84 ±3	112 ±3	140 ±3	168 ±3	182 ±1	224 ±3	280 ±3	336 ±3	364 ±3		
Immunology and Other Labs																
Lymphocyte subtypes and FACS panel ^q		x ⁿ	x ⁿ	x	x		x		x ⁿ	x ⁿ		x		x	x	x
Quantitative Ig ^r		x					x		x			x		x		x
Autoantibodies ^s		x			x				x			x		x	x	x
HACA		x							x					x	x	x
PK samples		x ^t	x ^t	x	x		x		x ^t	x ^t	x	x	x	x	x	
Optional serum biomarker sample for RCR		x ^u		x	x		x		x ^u	x ^u				x	x	
Optional whole blood sample (RNA) for RCR		x ^u		x	x		x		x ^u	x ^u				x	x	
Optional whole blood sample (DNA) for RCR ^v		x														

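### The SAP tie rule makes the Week 2, 24 and 26 by-visit laboratory and lymphocyte values post-infusion samples, drawn after premedication that differs by arm

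*SAP*

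**What the plan says.** **Sampling.** In the protocol's Appendix 1 (repeated in SAP Appendix 3), haematology, blood chemistry and the lymphocyte/FACS panel carry footnote n at Weeks 1, 2, 24 and 26. The footnote reads: "Samples to be collected prior to administration of IV methylprednisolone or saline solution and 30 minutes following completion of rituximab or rituximab placebo infusion". Footnote o confirms the second chemistry sample by leaving out one analyte from it: "glucose (except at 30 minutes following completion of study drug infusion at Weeks 1, 2, 24, and 26". Quantitative immunoglobulins do not carry footnote n.

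**Premedication.** Under protocol 4.3.2.1 the IV premedication is methylprednisolone 100 mg in the rituximab arm and saline in the MMF arm. It is to be finished at least 30 minutes before the infusion starts.

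**Assignment to visits.** SAP 4.6 says data are "mapped to visits that appear in the schedule of assessments per the protocol using the actual study day of assessment". SAP 4.10.2 defines study day as a difference of dates. SAP 4.10.3, which covers summaries displayed by visit, takes the value nearest the nominal timepoint and then adds: "If two values are equidistant from the nominal timepoint then the latest value will be selected".

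**Use.** SAP 4.9.4.1 summarises laboratory parameters by visit. SAP 4.9.4.3 says: "The absolute, change and percent change from baseline values will be summarized by visit and treatment group for the above lymphocyte populations". It also gives the proportions below the lower limit of normal for CD3, CD4, CD8 and CD19 by visit and arm. Neither section separates pre- from post-infusion samples. PK is different: SAP 4.8 reports it by nominal time of collection.

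**The concern.** A by-visit laboratory comparison is readable only if the sample is taken under the same conditions in both arms, and under the same conditions as baseline. Here the tie rule selects a sample taken a few hours after an IV steroid in one arm and after saline in the other. Baseline is protected, because SAP 4.10.2 makes it the last value before study treatment. Change from baseline at Weeks 2, 24 and 26 therefore sets a pre-premedication value against a post-infusion value.

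The protocol accepts that corticosteroids can move these counts. Section 1.2.5 says of RA patients: "T-cell counts remained stable after a transient decrease, likely because of concomitant RA treatment with corticosteroids". A between-arm difference in lymphocytes, T-cell subsets, neutrophils or chemistry at these visits could therefore combine study-drug effect with an acute premedication or infusion effect.

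Week 24 raises a second question. The pre-infusion CD19 count on Day 168 describes B-cell status before the second course, and the selected sample comes after re-dosing has begun.

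**Working it through.** The plan states no figure to reproduce. The check applies its rules to its own schedule.

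**1. Visit windows.** SAP 4.6 places window limits at the midpoint between consecutive scheduled days for each variable; as in SAP Table 1, the first post-baseline window opens after Day 1.

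- Week 2 (Day 15): upper limit (15 + 28)/2 = 21.5.
- Week 24 (Day 168): (112 + 168)/2 = 140 to (168 + 182)/2 = 175.
- Week 26 (Day 182), haematology and chemistry: 175 to (182 + 224)/2 = 203.
- Week 26, lymphocytes (next scheduled visit Day 280): 175 to (182 + 280)/2 = 231.

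**2. Distance of the two samples.** Both are taken on the same study day d. Distance from the nominal day D is |d − D| for each, so they tie whatever the visit offset. The permitted offsets are ±1 day at Week 2, ±3 at Week 24 and ±1 at Week 26, which gives 3 + 7 + 3 = 13 cases.

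| Visit | Offsets checked | Tie | Sample selected |
|---|---|---|---|
| Week 2 | 3 | 3 of 3 | post-infusion |
| Week 24 | 7 | 7 of 7 | post-infusion |
| Week 26 | 3 | 3 of 3 | post-infusion |

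The result is 13 of 13 for haematology and chemistry, and 13 of 13 for lymphocytes. Glucose keeps its pre-infusion value, because it is not measured afterwards.

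**3. Share of visits.** Post-baseline lymphocyte visits are Weeks 2, 4, 8, 16, 24, 26, 40 and 52, so 3 of 8 are affected. Haematology and chemistry add Weeks 32 and 48, so 3 of 10 are affected.

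**4. Time since premedication.** Protocol Appendix 3 gives planned infusion lengths of 255 minutes (Day 168, using the Day 1 schedule) and 195 minutes (Days 15 and 182). The minimum interval from the end of premedication to the second sample on those schedules is:

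- Day 168: 30 + 255 + 30 = 315 minutes.
- Days 15 and 182: 30 + 195 + 30 = 255 minutes.

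**5. Oral steroid background.** Under protocol Table 1, a patient without disease activity who starts at 80 mg spends one week at 80 and one at 60, and reaches the 40 mg step at Day 15. A patient who starts at 60 mg reaches the 30 mg step. This holds in both arms. By Week 24 the target is 0 mg/day in both arms (protocol 3.1.2).

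**The case against.** **The tie depends on reading the rule in whole days.** The SAP does not define a nominal timepoint for infusion-day laboratory samples. Its Appendix 11 imputes times for laboratory records, so clock times exist, and PK on the same sampling pattern is reported by nominal collection time. The schedule also has a general note placing treatment-day assessments before dosing unless specified otherwise. A programmer could therefore set a pre-dose target time and pick the first sample. That is possible, but it needs a laboratory timepoint that the SAP never supplies. SAP 4.6 and its Table 1 use the scheduled day, and footnote n is itself one of the specified exceptions.

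**The steroid contrast is not steroid against none.** A reader might infer that only the rituximab arm is exposed to corticosteroid at these visits. The documents do not support that: at Week 2 both arms are on substantial oral prednisone, and the IV dose comes on top of it. The contrast is clearer at Weeks 24 and 26.

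**No effect size is available.** The T-cell remark in protocol 1.2.5 concerns RA treatment and not same-day sampling. A reader might also infer that Week 24 B-cell recovery is hidden and depletion overstated. That would need a material CD19 fall within 30 minutes of the end of the infusion. The protocol calls depletion rapid (1.2.1) and near-complete by 2 weeks after the first dose in RA (1.2.5), but gives no within-day figure. This part of the objection stands.

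**Worst-grade tables are a separate matter.** SAP 4.9.4.1 plans "shift tables from baseline to highest grade post-baseline", and SAP 4.10.3 does not govern those tables. Both arms contribute post-infusion samples on the same four days, and methylprednisolone is part of the rituximab regimen as given. Removing those samples could take acute abnormalities out of the main safety display. This also stands.

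**Conclusion.** The point holds as a flaw in a stated selection rule. Whenever both infusion-day samples are present and no other sample lies nearer the nominal day, the Week 2, 24 and 26 by-visit values for haematology, chemistry other than glucose, and lymphocyte subsets are post-infusion values. They follow different IV premedication in the two arms. This rests on the nominal timepoint being the scheduled study day, which is how SAP 4.6 works.

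The consequence is a possible confounding of unknown size and is best stated as such. It is most plausible at Weeks 24 and 26 and weaker at Week 2. For CD19 at Week 24, the documents support saying that status before the second course could be obscured. They do not support saying that it is.

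The reach is limited to descriptive safety and pharmacodynamic summaries. The primary endpoint and the five hierarchically tested secondary endpoints do not use these data.

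**What to change.** Add one sentence to SAP 4.10.3: for assessments sampled both before and after an infusion on the same day, the by-visit value is the pre-premedication sample. Summarise the 30-minute post-infusion values in their own table, by arm.

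Keep the post-infusion samples in the worst-grade and marked-abnormality tables. A supplementary display without them is optional.

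The cost is one SAP sentence and one extra table. Both samples are already scheduled, so no new data are needed. The follow-up SAP states that the Week 52 analyses have been completed; for those outputs the same split can be produced as a supplementary display.

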4.10.4 Missing Data

Methods for handling missing data for efficacy analyses are described in detail throughout Section 4.7. Missing or partial dates for AEs, concomitant medications (except oral corticosteroids), laboratory assessments, and medical history will be imputed as detailed in [Appendix 11](#).

